## 11.0 Study Timelines

11.1 Describe the anticipated duration needed to enroll all study subjects.

Response: Accrual is expected to be at the rate of 1 subject weekly, thus we should complete enrollment in approximately 18-20 months. We expect to complete all study activities in 30 months.

11.2 Describe the duration of an individual subject's participation in the study. Include length of study visits, and overall study follow-up time.

Response: 12 Weeks

11.3 Describe the estimated duration for the investigators to complete this study (i.e. all data is collected and all analyses have been completed).

Response: 30 Months

## 12.0 Setting

12.1 Describe all facilities/sites where you will be conducting research procedures. Include a description of the security and privacy of the facilities (e.g. locked facility, limited access, privacy barriers). Facility,

department, and type of room are relevant. Do not abbreviate facility names.

*NOTE: Examples of acceptable response may be: "A classroom setting in the Department of Psychology equipped with a computer with relevant survey administration software," "The angiogram suite at Buffalo General Medical Center, a fully accredited tertiary care institution within New York State with badge access," or, "Community Center meeting hall."*

Response: Research will be conducted at the Diabetes Endocrinology Research Center of WNY, located at [name] and at the CTRC located in [name]. The Diabetes Research Center has facilities and exam rooms available for insulin pump download, CGM device download, meal and infusion studies and presence of study coordinator and registered nurse for data collection and blood work at all times. One of the investigators will be available at all times to address patients' related issues. CTRC location is a fully equipped laboratory with equipment including ultra-low freezers for sample storage, centrifuges, microscopes for sample preparation, infusion pumps, ELISA, PCR and immunoblotting instrumentation. Patients will also be consented at UBMD Pediatrics. [name]. Once patients review the consent, and all of their questions are answered, they will be asked to sign the consent. They will then be asked to come to the Diabetes Research Center to be screened and partake in the study. UBMD Pediatrics will only be used as a site for recruiting and consenting; no study procedures will take place here.

12.2 For research conducted outside of UB and its affiliates, describe:

- Site-specific regulations or customs affecting the research
- Local scientific and ethical review structure

*NOTE: This question is referring to UB affiliated research taking place outside UB, i.e. research conducted in the community, school-based research, international research, etc. It is not referring to multi-site research. UB affiliated institutions include Kaleida Health, ECMC, and Roswell Park Cancer Institute.*

Response:

- N/A: This study is not conducted outside of UB or its affiliates.

## 13.0 Community-Based Participatory Research

13.1 Describe involvement of the community in the design and conduct of the research.

*NOTE: Community-Based Participatory Research (CBPR) is a collaborative approach to research that equitably involves all partners in the research process and recognizes the unique strengths that each brings. CBPR begins with a research topic of importance to the community, has the aim of combining*

*knowledge with action and achieving social change to improve health outcomes and eliminate health disparities.*

Response:

N/A: This study does not utilize CBPR.

*13.2 Describe the composition and involvement of a community advisory board.*

Response:

N/A: This study does not have a community advisory board.

## **14.0 Resources and Qualifications**

*14.1 Describe the qualifications (e.g., education, training, experience, expertise, or certifications) of the Principal Investigator **and** staff to perform the research. When applicable describe their knowledge of the local study sites, culture, and society. Provide enough information to convince the IRB that you have qualified staff for the proposed research.*

*NOTE: If you specify a person by name, a change to that person will require prior approval by the IRB. If you specify a person by role (e.g., coordinator, research assistant, co-investigator, or pharmacist), a change to that person will not usually require prior approval by the IRB, provided that the person meets the qualifications described to fulfill their roles.*

Response: All study personnel are educated, trained, and licensed as required for their delegated role in this study. All study personnel have also received the required university training and will be trained by the PI before the study starts

***Describe other resources available to conduct the research.***

*14.2 Describe the time and effort that the Principal Investigator and research staff will devote to conducting and completing the research.*

*NOTE: Examples include the percentage of Full Time Equivalents (FTE), hours per week. The question will elicit whether there are appropriate resources to conduct the research.*

Response: The principal investigator supervises the research project and weekly research meetings are conducted to discuss the recruitment rate, resolve and discuss issues related to the conduct, safety, analysis of the study and related publications. PI is expected to spend 5% of his academic time on this research. The co-investigators and study coordinator provide coverage to the research related activity for 365 days a year.

14.3 Describe the availability of medical or psychological resources that subjects might need as a result of anticipated consequences of the human research, if applicable.

*NOTE: One example includes: on-call availability of a counselor or psychologist for a study that screens subjects for depression.*

Response: Available medical literature will be provided as deemed appropriate or requested by patient through UB libraries, Pubmed, Google scholar as all the investigators have access to medical literature through listed resources above

The patient will also have access to physician (Investigators and Co-Investigators) who will be available to address any adverse effects or other questions during the course of the study who will be available to address any adverse effects or other questions during the course of the study

14.4 Describe your process to ensure that all persons assisting with the research are adequately informed about the protocol, the research procedures, and their duties and functions.

Response: Education through training meetings, conferences and discussions

## 15.0 Other Approvals

15.1 Describe any approvals that will be obtained prior to commencing the research (e.g., school, external site, funding agency, laboratory, radiation safety, or biosafety).

Response: NA

N/A: This study does not require any other approvals.

## 16.0 Provisions to Protect the Privacy Interests of Subjects

16.1 Describe how you will protect subjects' privacy interests during the course of this research.

*NOTE: Privacy refers to an individual's right to control access to him or herself. Privacy applies to the person. Confidentiality refers to how data collected about individuals for the research will be protected by the researcher from release. Confidentiality applies to the data.*

*Examples of appropriate responses include: "participant only meets with a study coordinator in a classroom setting where no one can overhear", or "the participant is reminded that they are free to refuse to answer any questions that they do not feel comfortable answering."*

Response: Our clinical providers involved in the study will identify potential patients for recruitment from the Diabetes-Endocrinology Center of WNY Clinics according to the inclusions and exclusion criteria and through advertisements. Patient who qualify will be

asked in private during their one on one consultation time with the physician if they wish to participate in the research study. If the patient agrees, the research coordinator will contact them for a telephone screening privately. The patients who call for potential participation in the study due to advertisement flyers will be screened over the phone with the research coordinator, using our telephone screening form.

When the patient is being seen at our clinics for the first time they sign the “Consent to use and disclosure of protected health information” form which clearly states that their protected health information (PHI) can be used for review in preparation for possible research.

If the patient passes the telephone screening, they will be asked to make an appointment to review and sign the consent. Patient will do this in a private, screen off area of the research department and will be allowed to discuss the consent in detail with the research coordinator and or study doctor. Patient will be no notified that it is completely voluntary to participate in the research study and can withdraw at any time.

We will not be accessing any medical information of the patients for whom the services are not provided by our clinic providers.

16.2 *Indicate how the research team is permitted to access any sources of information about the subjects.*

*NOTE: Examples of appropriate responses include: school permission for review of records, consent of the subject, HIPAA waiver. This question **does apply** to records reviews.*

Response: Consent of the subject and partial HIPAA waiver.

## 17.0 Data Management and Analysis

17.1 *Describe the data analysis plan, including any statistical procedures. This section applies to both quantitative and qualitative analysis.*

Response: **DATA ANALYSIS**

This is a prospective study to evaluate ketogenic stress before and after 12 week treatment with dapagliflozin and exenatide/Bydureon. The similarities in baseline values between the study groups will be compared using appropriate parametric tests. Transformations of the data on order to meet statistical assumptions may be considered. All statistical analysis will be carried out using SPSS software (SPSS Inc, Chicago, Illinois) based on intention to treat principle. Data will be presented as mean± standard error. *Data will not be imputed to replace missing data and only observed data will used to run the mixed model for repeated measurement (MMRM) analysis. The primary endpoint of the study is to detect a significant difference in the percent change in beta-hydroxybutyrate and acetoacetic acid (total ketone bodies) in the plasma samples following 12 weeks of dapagliflozin treatment compared to placebo. *Fasting samples collected at weeks 0, 1, 4, 8 and 12 will be used for this comparison with values at week 0 considered as baseline. The statistical analysis will be done using MMRM with assigned  $\alpha$  value of 0.05. There is no previous data on effects of dapagliflozin alone on ketone bodies generation in T1D but our preliminary data on 12 weeks treatment with**

dapagliflozin in patients with T1D using insulin and liraglutide shows more than a 2 fold increase in total ketone bodies.

The secondary end points include the *comparison of the acute changes in AUC0hr-6hr of ketone bodies (plasma and urine), FFA and glucagon between dapagliflozin, exenatide, combination of both and placebo before and after 12 weeks of treatment period using Paired t-test for within group comparisons and student t-test for between groups comparisons.* Additional secondary end points include comparison of basal plasma glucagon, FFA and urinary ketone bodies changes after 12 weeks of dapagliflozin and Bydureon or combination of both treatments compared to baseline using paired t-test and to placebo using 2-way RMANOVA. Changes in insulin dose, glucose levels and carbohydrate intake will be compared after 12 weeks of dapagliflozin and Bydureon treatments to baseline using paired t-test and to placebo with 2-way RMANOVA. Changes in lipolysis mediator (HSL) in plasma and expression of HSL and SGLT-2 in adipose tissue and MNC will be compared to baseline using paired t-test and to placebo with t-test.

*17.2 If applicable, provide a power analysis.*

*NOTE: This may not apply to certain types of studies, including chart/records reviews, survey studies, or observational studies. This question is asked to elicit whether the investigator has an adequate sample size to achieve the study objectives and justify a conclusion.*

*Response:* Conservatively estimating a difference in the change from baseline in ketone bodies generation between the dapagliflozin and placebo of 50%, with standard deviation of no more than 50%, a sample size of 20 patients per group (assuming a drop-out rate of 15%) should provide adequate power ( $\beta = 0.2$ ) to detect a significant difference ( $\alpha = 0.05$ ). A total of 80 patients will be recruited for the study.

*17.3 Describe any procedures that will be used for quality control of collected data.*

*Response:* Data will not be imputed to replace missing data and only observed data will be used to run the mixed model for repeated measurement (MMRM) analysis

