## 4.0 Study Design

### 4.1 Describe and explain the study design (e.g. case-control, cross-sectional, ethnographic, experimental, interventional, longitudinal, observational).

*Response:* The first 60 patients (cohort 1) will be involved in a single center, prospective, double blind, randomized, placebo –controlled in a parallel design study. The last 20 patients (cohort 2) will be enrolled into a single centered, prospective, randomized, open labeled study. The study will be conducted at the Diabetes – Endocrinology Center of Western New York under the direction of [name], M.D, [name], MD, [name] and [name], PhD.

In the first cohort, sixty (60) patients with T1D will be enrolled and randomized into 4 groups (15 each) to receive placebo, or dapagliflozin, or exenatide (5µg acutely)/Exenatide extended release (2mg weekly subcutaneous injection, long term), or exenatide (5µg acutely)/Exenatide extended release (2mg weekly subcutaneous injection, long term) and dapagliflozin treatments acutely and for 12 weeks.

The treatment arms of this study are:

1. Placebo Arm: dapagliflozin placebo (oral tablet) and exenatide (5µg acutely)/Exenatide extended release (long term) placebo (subcutaneous injection)
2. Dapagliflozin Arm: dapagliflozin 10mg (oral tablet) and exenatide (5µg acutely)/Exenatide extended release (long term) placebo (subcutaneous injection)
3. Exenatide/Exenatide extended release Arm: subcutaneous injection of Exenatide (5µg acutely)/Exenatide extended release 2 mg weekly injection (long term) and dapagliflozin placebo
4. Exenatide/Exenatide extended release & dapagliflozin Arm: Exenatide (5µg acutely)/Exenatide extended release 2 mg weekly injection (long term) and dapagliflozin 10mg

In the second cohort, twenty (20) patients will be randomized into three groups.

1. Open-label Dapagliflozin
2. Open-label Bydureon/Byetta
3. Open label Bydureon/Byetta and open label Dapagliflozin

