Response: The independent clinician monitor along with the principal investigator [name], PhD and co-investigators, [name], MD, [name], MD* and [name] will review the data at the completion of all visits by each subject and every 3 months to assess the safety and any potential risks to the participants. Furthermore they will also assess other risks including the physical, psychological, social, legal and economic harm to these patients. The investigators listed above will carefully watch for any invasion of privacy and breach of confidentiality. The principal investigator will be sharing the results of safety analysis of the study with the sponsor (AZ) and with the IRB. The study groups will remain blinded. If there are any safety concerns then co-investigator [name] who is not directly involved with the study participants will unblind the study groups on the discretion of principal investigator and present the analyzed data to the clinician monitor and investigators.

*19.7 Describe the frequency or periodicity of review of cumulative safety data.*

*Response: Safety data will be reviewed every 3 months. Study endpoint data will be reviewed once after half of the recruited patients have completed the study and then at the end of the study.*

*19.8 Describe the statistical tests for analyzing the safety data to determine whether harm is occurring.*

Response: The statistical analysis will be carried out using the student t-test or Wilcoxon's test for paired data

*19.9 Describe any conditions that trigger an immediate suspension of the research.*

Response:

1. Any episode of DKA occurring in >15% (placebo-adjusted) of participants.
2. Pancreatitis occurring in > 5 % (placebo-adjusted) of participants
3. New information becoming available concerning the safety of study drugs
4. Termination of funding.

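### The primary MMRM of percent change in ketones has no stated baseline covariate or model terms, and the 80% power claim assumes more placebo patients than the design supplies

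*Combined protocol and SAP*

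**What the plan says.** Section 17.1 defines the primary endpoint as to "detect a significant difference in the percent change in beta-hydroxybutyrate and acetoacetic acid (total ketone bodies) in the plasma samples" after 12 weeks of dapagliflozin compared with placebo. Fasting samples from weeks 0, 1, 4, 8 and 12 enter an MMRM at alpha 0.05, "with values at week 0 considered as baseline". No fixed effects, covariates, covariance structure or target contrast are given. On scale, the section adds: "Transformations of the data on order to meet statistical assumptions may be considered".

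Section 17.2 assumes a 50% difference in change from baseline "with standard deviation of no more than 50%, a sample size of 20 patients per group (assuming a drop-out rate of 15"%), for 80% power at alpha 0.05. It gives no source for the SD. Section 17.1 says: "There is no previous data on effects of dapagliflozin alone on ketone bodies generation in T1D". It cites the pilot only for the size of the rise.

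On numbers, section 4.1 says of cohort 1: "sixty (60) patients with T1D will be enrolled and randomized into 4 groups (15 each"), one of the four groups being placebo. It then says: "In the second cohort, twenty (20) patients will be randomized into three groups". All three of those groups are open-label active treatment.

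Section 19.7 says: "Study endpoint data will be reviewed once after half of the recruited patients have completed the study".

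**The concern.** Percent change divides by the patient's own fasting value, which is small here: the pilot means in section 3.1 sum to 0.11 + 0.32 = 0.43 mM at baseline. A patient who starts low by chance tends to show a large percent rise, so percent change is usually negatively correlated with baseline. A model without baseline leaves that variation in the error term. The plan collects the week-0 value but does not say that the model uses it.

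Two things are at stake. The first is power, in a comparison with few placebo patients. The second is prespecification: as written, the covariate and the use of a transformation could be settled after the endpoint review at half of completers.

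The sample-size statement bears on the same comparison. If the placebo group is smaller than section 17.2 assumes, the stated power is not delivered even when the SD assumption is right, and that assumption has no stated source.

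**Working it through.** **1. The plan's own figure.** Inputs from section 17.2: difference 50, SD 50, alpha 0.05 (taken as two-sided), power 0.80, dropout 15%. The noncentral t power uses ncp = 50 / (SD × √(1/n₁ + 1/n₂)) and df = n₁ + n₂ − 2. With 16 per arm power is 0.781. With 17 per arm, ncp = 1/√(2/17) = 2.92 and power is 0.807. Then 17/0.85 = 20 per group, so the stated number reproduces.

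**2. Numbers the design supplies (section 4.1).**
- Placebo: 15 × 0.85 = 12.75, about 13.
- Dapagliflozin, cohort 1 alone: also about 13.
- Dapagliflozin with cohort 2 pooled: 15 + 20/3 = 21.7, × 0.85 = 18.4, about 18. Equal allocation in cohort 2 is an assumption.

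| Completers (placebo v dapagliflozin) | ncp at SD 50 | SD 40 | SD 50 | SD 60 | SD 75 | Largest SD for 80% power |
|---|---|---|---|---|---|---|
| 17 v 17 (as in 17.2) | 2.92 | 0.94 | 0.81 | 0.65 | 0.47 | 50.5 |
| 13 v 18 (pooled) | 2.75 | 0.91 | 0.76 | 0.60 | 0.43 | 47.4 |
| 13 v 13 (cohort 1) | 2.55 | 0.86 | 0.69 | 0.53 | 0.37 | 43.7 |

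**3. How firm the 50% bound is.** The pilot spreads in section 3.1 are not labelled. Section 17.1 says the trial's own data will be shown as mean ± standard error, which favours reading them as SEs. On that reading (n = 10, SD = SE × √10) total ketones have a CV of about 0.68 to 0.81 before treatment and 0.49 to 0.69 after, depending on the unknown correlation between the two ketones. A lognormal model with no treatment shift then gives a percent-change SD of 70 to 94% at a baseline-to-follow-up correlation of 0.5, 51 to 64% at 0.7 and 30 to 33% at 0.9. The bound would hold only at high correlation. The documents do not give that correlation.

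**4. What the covariate adds at the plan's own SD.** The residual SD is 50 × √(1 − r²), with r the correlation of baseline with percent change. For 17 v 17, power is 0.81 at r = 0, 0.84 at 0.3, 0.90 at 0.5 and 0.98 at 0.7.

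**5. Simulation.** Assumptions: lognormal data, one post-baseline value standing in for the week-12 contrast, 1.5-fold effect, log-scale correlation 0.6, 17 v 17, 8,000 runs per row. Repeat runs differ by one or two points.

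| Log SD, baseline then follow-up | Percent change | Percent change + log baseline | Log change | Log ANCOVA |
|---|---|---|---|---|
| 0.67 then 0.55, both arms | 0.48 | 0.63 | 0.54 | 0.73 |
| 0.67 throughout | 0.43 | 0.49 | 0.49 | 0.56 |
| 0.55 throughout | 0.59 | 0.67 | 0.64 | 0.72 |
| 0.67; placebo stays at 0.67, dapagliflozin falls to 0.55 | 0.42 | 0.52 | 0.51 | 0.63 |

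The 0.67 and 0.55 come from the SE reading, with an assumed correlation of 0.5 between the two ketones. With equal SDs throughout, the covariate adds 6 to 8 points here; at 13 v 13 with 0.67 throughout it adds about 4 (0.33 to 0.37). At 13 v 18 and correlations of 0.5 to 0.8, it adds 1 to 10 points with equal log SDs of 0.5 to 0.6, and 10 to 22 with the SE-based SDs. Gains approach zero where power is already near 1. Type I error at 13 v 18 was 0.043 to 0.052 across the methods.

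**The case against.** **The scale is already prespecified.** This stands. A reader might infer from the transformation clause that the outcome scale is open. Percent change is named, and the clause is limited to meeting statistical assumptions. What is missing is a rule for when a transformation would be used, and the model terms.

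**The largest gains rest on a favourable example.** This also stands. A reader might take the first row of the simulation table, with +15 points for the covariate and +25 for log ANCOVA, as the expected benefit. That row applies a follow-up SD of 0.55 to both arms, but in the pilot that spread was seen after dapagliflozin. Nothing in the documents supports a falling SD on placebo. With equal SDs the gains shrink to 6 to 8 and about 13 points.

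**The benefit may not matter.** Section 17.2 calls its difference conservative, and the pilot rise was 0.92/0.43 = 2.14-fold. At that effect (13 v 18, correlation 0.6, SE-based SDs) percent change without a covariate already has power of about 0.90, against 0.99 for log ANCOVA. If the pilot spreads are SDs, every method has at least 0.99 at that effect. So the gain depends on conditions, but the covariate costs nothing.

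**A log analysis answers a different question.** It estimates a ratio of geometric means, so its higher power is not a like-for-like gain. The documents do not support replacing the sponsor's endpoint on that ground.

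**Conclusion.** The point holds as one of efficiency and prespecification, together with an overstated power figure. The sample-size arithmetic in section 17.2 is correct for its inputs, and nothing here shows percent change to be an invalid endpoint or to inflate type I error.

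- **Model.** Section 17.1 leaves the baseline covariate and all model terms unstated. Under the assumed lognormal data and a 1.5-fold effect, the covariate is worth about 0 to 22 points of power, typically 4 to 8 with equal log SDs and correlation 0.6. The size rests on a log SD and a correlation that the documents do not give.
- **Power.** With 15 placebo patients and 15% dropout, power at SD 50% is about 0.69 (13 v 13), or about 0.76 (13 v 18) if cohort 2 is pooled, not 0.80. This needs no distributional assumption beyond the plan's own t-test framework. The pooled figure also assumes roughly equal allocation in cohort 2.

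The pooled figure covers precision only. It compares a dapagliflozin group that is partly open-label and enrolled later with blinded placebo patients from cohort 1, so comparability would need its own justification.

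**What to change.** **Section 17.1.** Keep percent change as the primary endpoint. State that the MMRM contains treatment, visit, treatment-by-visit, the log week-0 total ketone value and its interaction with visit. Name the week-12 dapagliflozin-minus-placebo contrast as the test. Give the covariance structure with a fallback, the degrees-of-freedom method, and which arms and cohorts enter. Replace the optional transformation sentence with a prespecified sensitivity analysis: the same model on log ketones, reporting a geometric mean ratio with 95% CI and a rule for values below the assay limit.

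**Timing.** Fix this before the endpoint review at half of completers in section 19.7. The documents do not show whether that review has happened. If it has, date the change, say what had been seen, and report the unadjusted percent-change result alongside.

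**Section 17.2.** Restate power with the actual placebo number: about 0.69 for cohort 1 alone, or about 0.76 if cohort 2 is pooled, and say which applies. Give the basis for the 50% SD, say whether the pilot spreads are SEs or SDs, and show power over a range of SDs (13 v 18: 0.91 at 40, 0.60 at 60, 0.43 at 75).

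**Cost.** A few sentences. No new data or visits are needed, and the model runs in SPSS. The covariate leaves the estimand unchanged. The log analysis has a different estimand, which is why it is placed as a sensitivity analysis.
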